10.3.2 Safety Analyses

All safety analyses will be performed on the treated population. See Table 10.3.2-1 for a description of the safety analyses.

Table 10.3.2-1: Safety - Statistical Analyses

Endpoint	Statistical Analysis Methods
Incidence of DLTs (Part 1 only), AEs, SAEs, AEs leading to discontinuation, and death AEs will be graded according to CTCAE v4.03	DLT rate by dose level, frequency distribution of treated participants with AE using the worst CTC grade. Participants will be counted only (1) once at the PT level, (2) once at the system organ class level, and (3) once in the "total participant" row at their worst CTC grade, regardless of system organ class or PT.
Incidence of treatment-related Grade 3-5 AEs within 24 weeks	Incidence rate (Part 2A, Part 2B) along with the ratio and difference in incidence rates (Part 2A) will be presented by point estimates and CIs ^a (Parts 2A and 2B)
Laboratory abnormalities Laboratory values will be graded according to CTCAE v4.03.	Laboratory shift table using the worst CTC grade on treatment per participant

Abbreviations: AE = adverse event; CTC = common terminology criteria; CTCAE = Common Terminology Criteria for Adverse Events; DLT = dose-limiting toxicity; PT = preferred term; SAE = serious adverse event.

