 - Participants with NSCLC will also be permitted in this portion of the study but not as part of the initial DLT assessment; instead, NSCLC participants will be evaluated only as part of adding additional participants to a previously tested cohort.
 - ii) Participants with Gastric, Esophageal, or Urothelial cancer:
 - 1) Gastric and esophageal cancer participants must have received, and then progressed, relapsed, or been intolerant to, at least 1 standard treatment regimen in the advanced or metastatic setting, if such a therapy exists.
 - 2) Urothelial carcinoma participants must have received, and then progressed, relapsed, been intolerant to, or ineligible for, at least 1 platinum-containing chemotherapy regimen.
 - iii) Participants with NSCLC:
 - 1) NSCLC participants must have received, and then progressed, relapsed, or been intolerant to, at least 1 standard treatment regimen in the advanced or metastatic setting, if such a therapy exists.
 - 2) If the tumor is PD-L1 >50% by immunohistochemistry (IHC), they may be treatment-naive.
 - iv) All Part 1B participants must be naive to prior anti-CTLA-4 and anti-PD-1 or anti-PD-L1 therapies.
 - v) Participants with CRC:
 - 1) Participants must have received and then progressed on or after, or have been intolerant or refractory to, at least 1 standard systemic therapy for metastatic and/or unresectable disease (or have progressed within 6 months of adjuvant therapy), including oxaliplatin and irinotecan.
 - 2) Participants must have known MSI-H or dMMR status. KRAS, and BRAF status, if known, should be documented.
 - 3) Participants who have received prior anti-angiogenic therapy (eg, bevacizumab) and/or anti epidermal growth factor receptor therapy (eg, cetuximab or panitumumab) are eligible.
 - vi) Participants with SCLC:
 - 1) Histologically or cytologically documented SCLC, limited or extensive stage disease
 - 2) Received at least 1 prior platinum-containing chemotherapy regimen.

vii) Participants with CRPC:

- 1) Participants must have at least 1 soft tissue lesion, unrelated to bone, that qualifies as measurable disease per RECIST v1.1.
- 2) Participants must have received and progressed/been intolerant of (or not be a candidate for) at least 1 and not more than 3 standard therapies and have been considered for all other potentially efficacious therapies.
- 3) Previous treatment for hormone sensitive prostate cancer does not qualify without subsequent treatment for hormone refractory state.

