7.5.1 Dose-limiting Toxicities

For the purpose of guiding dose escalation, DLTs will be defined based on the incidence, intensity, and duration of AEs that are possibly related to study treatment. The DLT period will be 5 weeks (35 days) in both BMS-986249 monotherapy and combination dose escalation (Parts 1A and 1B). Any toxicities that occur beyond the DLT period will be accounted for in making final dose level decisions. Participants who have received 2 doses of BMS-986249 and have completed or discontinued due to a DLT in the 5-week DLT period will be considered as DLT-evaluable participants for BMS-986249 monotherapy. Participants receiving either 2 dosing visits of

Protocol Amendment No.: 09

Date: 14-Mar-2023

BMS-986249 and nivolumab, or participants who discontinued due to a DLT in the 5-week combination treatment DLT period, will be considered as DLT-evaluable participants for combination treatment. Participants who withdraw from the study during the DLT evaluation period or have received less than 2 dosing visits for reasons other than a DLT in both monotherapy and combination therapy will not be considered as DLT-evaluable participants and may be replaced with a new participant at the same dose level. Participants who are dose delayed during the DLT evaluation period for reasons other than a DLT in both monotherapy and combination therapy will be considered as DLT-evaluable participants if they received at least 2 doses of therapy.

For the purpose of participant management, any drug-related AE that meets DLT criteria, regardless of the cycle or cohort (including Part 2) in which it occurs, will lead to discontinuation of study treatment. The incidence of DLT(s) during the 5-week DLT evaluation period will be used in dose escalation decisions and to define the MTD. AEs occurring after the DLT period will be considered for the purposes of defining the recommended Phase 2 dose of BMS-986249 (RP2D) upon agreement between the Sponsor, Medical Monitor (or designee), and investigators.

AEs will be graded according to the NCI CTCAE v4.03.

Part 1B participants with NSCLC will only be evaluated in a cohort once the initial DLT evaluation for that cohort has been completed.

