10.2 Populations for Analyses

For purposes of analysis, the populations are defined in Table 10.2-1.

Table 10.2-1: Populations for Analyses

Population	Description		
Enrolled	All participants who sign informed consent		
Randomized	All participants who are randomized to treatment arm (Part 2A)		
Treated	All participants who take at least 1 dose of study treatment		
Pharmacokinetic	All treated participants who have evaluable concentration-time data		
Immunogenicity	All treated participants who have baseline and at least 1 post-baseline pre-infusion immunogenicity assessment for the analyte evaluated		

Protocol Amendment No.: 09

Table 10.2-1: Populations for Analyses

Population	Description
Biomarker	All treated participants with available biomarker data.
Patient-reported outcome	All treated participants with patient-reported outcome data at baseline and at least 1 post-baseline assessment.

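### The Part 1 DLT rate by dose level is assigned to all treated participants, so early leavers whom the protocol calls not DLT-evaluable dilute the reported rate

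*Combined protocol and SAP*

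**What the plan says.** **The reporting rule.** Section 10.3.2 opens with "All safety analyses will be performed on the treated population". Table 10.2-1 (Section 10.2) defines treated as "All participants who take at least 1 dose of study treatment". The first row of Table 10.3.2-1 covers "Incidence of DLTs (Part 1 only), AEs, SAEs, AEs leading to discontinuation, and death", and the method given is "DLT rate by dose level, frequency distribution of treated participants with AE using the worst CTC grade". No separate denominator is named for the DLT rate. Table 10.2-1 has dedicated sets for PK, immunogenicity, biomarker and patient-reported data, but none for DLT evaluability.

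**The evaluability rule.** Section 7.5.1 sets a DLT period of 5 weeks (35 days). For monotherapy it counts as evaluable "Participants who have received 2 doses of BMS-986249 and have completed or discontinued due to a DLT in the 5-week DLT period"; for combination treatment the rule is framed in dosing visits. On the other side, "Participants who withdraw from the study during the DLT evaluation period or have received less than 2 dosing visits for reasons other than a DLT", under monotherapy or combination, "will not be considered as DLT-evaluable participants and may be replaced with a new participant at the same dose level".

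**The counting rule.** Section 10.1.1 requires at least 6 DLT-evaluable participants at the model-recommended MTD and allows at most 12 per dose level. It feeds the Bayesian model with DLT-period information. Sections 5.1.2.1 and 5.1.2.2 allow a fourth participant in each cohort (3 + 1) as cover for early losses.

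**Added participants.** Section 6.1 admits NSCLC participants to Part 1B "but not as part of the initial DLT assessment". Sections 5.1, 5.1.2.3 and 10.1.1 allow further participants at dose levels already found tolerable.

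**The concern.** The design expects some participants to be dosed and then lost before they can inform the DLT question, and it replaces them for that reason. The reporting rule keeps them. A participant who leaves on Day 10 with progressive disease is not DLT-evaluable under Section 7.5.1. Under Section 10.3.2 that person still counts as someone treated without a DLT, and the replacement is counted as well.

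Incidence of events meeting the DLT criteria is a primary endpoint of Part 1 (Table 4-1). Two things are at stake. The reported rate would be too low at any dose level that has both a DLT and a replaced participant. The table would also disagree with the evaluable counts on which the same cohort was judged during escalation.

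**Working it through.** The plan states no DLT rate, so there is no figure to reproduce. The check is simple arithmetic on the two denominators.

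**Inputs**
- x: number of DLTs in the 35-day period at a dose level. Illustrative.
- n: DLT-evaluable participants at that level. I use 3 (initial cohort size, Sections 5.1.2.1 and 5.1.2.2), 6 and 12 (minimum at the MTD and maximum per level, Section 10.1.1).
- m: treated participants who left or missed dosing for reasons other than a DLT. The documents do not give m; I assume 1 to 3.

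**Formulas**
- Rate on the evaluable set: x/n.
- Rate on the treated set: x/(n + m). By the Section 7.5.1 definition, the m participants contribute no DLT.
- Relative understatement: 1 − [x/(n + m)]/(x/n) = m/(n + m), for any x of 1 or more. With x = 0, both rates are 0.

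**Results**

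| n | x | x/n | m = 1 | m = 2 | m = 3 |
|---|---|---|---|---|---|
| 3 | 1 | 33.3% | 1/4 = 25.0% | 1/5 = 20.0% | 1/6 = 16.7% |
| 6 | 1 | 16.7% | 1/7 = 14.3% | 1/8 = 12.5% | 1/9 = 11.1% |
| 12 | 2 | 16.7% | 2/13 = 15.4% | 2/14 = 14.3% | 2/15 = 13.3% |

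Relative understatement, m/(n + m):
- n = 3: 1/4 = 25.0%, 2/5 = 40.0%, 3/6 = 50.0%
- n = 6: 1/7 = 14.3%, 2/8 = 25.0%, 3/9 = 33.3%
- n = 12: 1/13 = 7.7%, 2/14 = 14.3%, 3/15 = 20.0%

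**NSCLC and other added participants.** The formula does not cover them. They fall outside the initial DLT assessment because of tumour type or time of entry, not because they were free of a DLT. If y of k such participants have events that are counted, the pooled rate is (x + y)/(n + k). That is below x/n only when y/k is below x/n. The documents do not say whether their events count, so the direction is not determined.

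**Q8W cohorts.** The Section 7.5.1 monotherapy rule asks for 2 doses. At Q4W the second dose falls on Day 1 + 28 = 29, inside the 35-day period. At Q8W (Section 3.2.1.6; Appendix 12, where the second BMS-986249 dose is at Cycle 3 Day 1) it falls on about Day 1 + 56 = 57, outside it. The two passages do not fit together, which matters for any denominator built on Section 7.5.1.

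**The case against.** **The DLT rate is understood to use evaluable participants, and the SAP can say so.** Section 7.5.1 already defines who is evaluable. Section 10.3 calls itself a summary, with a Statistical Analysis Plan to be finalised before database lock. This softens the point but does not remove it. No separate SAP text is in the documents supplied. Section 10.3.2 covers all safety analyses without exception and defers nothing about DLTs, whereas the time-to-event, immunogenicity, ECG and further exploratory patient-reported outcome analyses are expressly deferred in part.

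**Escalation and the MTD/RP2D are unaffected.** A reader might infer that dose decisions are biased. The documents do not support that. The MTD comes from a posterior-probability criterion in the Bayesian model, and the final MTD/RP2D from that recommendation plus an overall clinical assessment (Section 10.1.1), not from the Section 10.3.2 table. Section 3.2.1.6 also reports that no MTD has been reached. This objection stands in full.

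**A crude rate that falls below 16% changes nothing.** Moving from 16.7% to 14.3% looks like leaving the target interval in Section 10.1.1. But 16% is an edge of an interval inside a posterior-probability statement, and no rule compares a crude rate with it. The crossing should not be used as an argument.

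**The bias is not always downward.** A reader might conclude that every non-evaluable participant lowers the rate. That is certain only for early leavers and those who missed dosing. It does not extend to NSCLC or other added participants, as shown above. Nor does Section 10.3.2 limit the numerator to 35 days; if later events were counted, the treated-set rate could exceed the evaluable-set rate. The claim is therefore confined to the DLT-period rate and to participants excluded by Section 7.5.1.

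**A 35-day rate may not match the model inputs either.** Section 10.1.1 lets events outside the window be incorporated into the model. That is so, and it is a reason to tabulate later events separately.

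**Conclusion.** The point holds as a fault in a stated rule for a primary Part 1 endpoint. Where a dose level has at least one DLT and m participants excluded by Section 7.5.1, the reported DLT-period rate is too low by m/(n + m) in relative terms. For an assumed m of 1 to 3 this is 25–50% with 3 evaluable participants, 14–33% with 6 and 8–20% with 12. With no DLT or no such participant at a dose level, this mechanism has no effect. The actual size is unknown because the documents give neither count.

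The consequence is limited to the reported table and its agreement with the evaluable counts used in escalation. For NSCLC and other added participants the present rule pools people outside the initial DLT assessment, with an effect of unknown sign; that is a reason to define the set, not evidence of understatement. The change should be made, and it is inexpensive.

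**What to change.** 1. Add a DLT-evaluable population to Table 10.2-1, based on Section 7.5.1.
2. In Section 10.3.2, use that population for the DLT rate by dose level, with DLTs in the 35-day DLT period as the numerator. Keep the treated population for every other safety row.
3. Tabulate separately, in treated participants, DLT-criterion events after Day 35 and those in NSCLC or other added participants outside the initial DLT assessment.
4. Before applying the new set to Q8W cohorts, reconcile the 2-dose monotherapy wording in Section 7.5.1 with the Q8W schedule. Which wording should give way is for the sponsor to settle.

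The cost is one population row, a short change to Section 10.3.2 and the Q8W reconciliation. No new data are needed. The downside is that reported DLT rates may look slightly less favourable.

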10.3.3 Pharmacokinetic Analysis for BMS-986249

PK analyses are described in Table 10.3.3-1.

Table 10.3.3-1: Pharmacokinetic - Statistical Analyses

Endpoint	Statistical Analysis Methods
Cmax, AUC(0-T), AUC(TAU), Ctau, CLT, Css-avg, AI_Cmax, AI_AUC, and T-HALF	Summary statistics: geometric means and coefficients of variation
Cmax, AUC(0-T), and AUC(TAU)	Scatter plots versus dose for each cycle measured; dose proportionality based on a power model and a CI around the power coefficient
Tmax	Summary statistics: medians and ranges
Ctrough	Summary statistics to assess attainment of steady state: geometric means and coefficients of variation, by treatment and by day; plots versus time by dose

Abbreviations: AI_AUC = ratio of an exposure measure at steady state to that after the first dose (exposure measure includes AUC[TAU]); AI_Cmax = ratio of an exposure measure at steady state to that after the first dose (exposure measure includes Cmax); AUC(0-T) = area under the blood concentration-time curve from time zero to time of last quantifiable concentration (may be calculated if concentrations are not quantifiable up to TAU across a treatment group); AUC(TAU) = area under the concentration-time curve in 1 dosing interval; CLT = total body clearance; Cmax = maximum observed concentration; Css-avg = average blood concentration over a dosing interval (AUC[TAU]/tau) at steady state; Ctau = observed blood concentration at the end of a dosing interval; Ctrough = trough observed blood

Protocol Amendment No.: 09

^a Safety analyses will be executed with an 80% two-sided CI for primary endpoint of related Grade 3-4 AE rates.

concentrations (this includes predose concentrations [C0] and Ctau); T-HALF = terminal blood half-life; Tmax = median time of maximum observed concentration.

PK concentration-time data for ipilimumab and/or nivolumab may be pooled with data from other studies for integrated PPK and exposure analyses, which will be presented in a separate report.

10.3.4 Immunogenicity

Immunogenicity analyses are described in Table 10.3.4-1.

Table 10.3.4-1: Immunogenicity - Statistical Analyses

Endpoint	Statistical Analysis Methods
Incidence of ADA	Frequency distribution of baseline
Baseline ADA-positive participant is defined as a participant who has an ADA-detected sample at baseline ^{a,b}	ADA-positive participants and ADA-positive participants after initiation of the treatment for each analyte
ADA-positive participant is a participant with at least 1 ADA-positive sample relative to baseline after initiation of the treatment	

Abbreviation: ADA = anti-drug antibody.

10.3.5 Biomarker Analyses

Biomarker statistical analyses are described in Table 10.3.5-1.

Table 10.3.5-1: Biomarker - Statistical Analyses

Endpoint	Statistical Analysis Methods

10.3.6 ECG Analyses

All ECG data analyses, including summaries of each ECG parameter, frequency distribution of participants' maximum values/changes, and scatter plots, will be performed following the current practice of ECG data analysis. Concentration-response analysis may be performed using mixed effect model, if appropriate, for participants with time matched ECG and PK data collection (Part 1A). The details of ECG data analysis will be provided in the Statistical Analysis Plan.

^a Baseline sample is the last sample before initiation of the treatment.

b Details of the immunogenicity data analysis, including ADA titers, will be provided in the Statistical Analysis Plan.

10.3.7 Patient-Reported Outcome Analyses

PRO analyses are described in Table 10.3.7-1.

Table 10.3.7-1: PRO - Statistical Analyses

[figure not shown]
Secondary Endpoint	Statistical Analysis Methods
To evaluate TTD in Global Health Status/QoL of the EORTC QLQ-C30 (Part 2A only)	TTD in Global Health Status/QoL and Physical Functioning will be defined as the time from randomization until a clinically meaningful decline (ie, reduction ≥10 points) from baseline in EORTC QLQ-C30 global health/quality of life subscale score and Physical Functioning Scale score. Estimates for both Global Health Status/QoL and Physical Functioning will be provided with associated 95% CIs.
To evaluate TTD in Physical Functioning Scale of the EORTC QLQ-C30 (Part 2A only)	The analysis will use all available data from randomized participants, including data collected during post-treatment follow up. Median deterioration times, hazard ratios, and 95% CIs will be calculated

Abbreviations: CI = confidence interval; EORTC = European Organisation for Research and Treatment of Cancer; PRO = patient-reported outcome; QLQ-C30 = Quality of Life Questionnaire – Core 30; QoL = quality of life; TTD = time to deterioration.

Analyses of PRO will be performed on participants who have an assessment at baseline and at least 1 post-baseline assessment.

Further exploratory analyses for Part 2A and Part 2B not specified here will be described in the Statistical Analysis Plan, which will be finalized before database lock and may be presented separately from the main clinical study report.

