2 SCHEDULE OF ACTIVITIES

Study assessments and procedures are shown in Table 2-1, Table 2-2, Table 2-3, Table 2-4, and Table 2-5.

In limited instances, scheduled events (including events other than safety assessments) can occur outside of the indicated timeframes but the Sponsor should first be notified.

If a participant has a delay in study treatment administration for any reason, then assessments and laboratory tests (with the exception of any tests needed to ensure participant safety) should be correspondingly delayed with the exception of tumor assessments. Tumor assessments continue per protocol schedule regardless of any treatment delay incurred.

The pharmacokinetic (PK), and safety profiles of BMS-986249 are being elucidated, modifications to the procedures (ie, reduction in PK, sampling, timing of procedures, dose schedules) currently outlined in Section 2 and Section 9 may be required. These modifications will not include the addition of new procedures and will be documented in a note to file or administrative letter.

In the event that multiple procedures are required at a single time point, the electrocardiogram (ECG) may be obtained up to 15 minutes earlier, vital signs may be obtained up to 10 minutes earlier or later, and clinical laboratory samples may be obtained up to 5 minutes earlier than the nominal time point, ensuring the PK samples can be collected on time.

 Table 2-1:
 Screening Schedule of Activities for All Study Parts

Procedure	Screening Visit (Days -30 to -1)	Notes					
Eligibility Assessments							
Informed Consent	X	Must be obtained prior to performing any screening procedures. A participant is considered enrolled only when a protocol-specific ICF is signed.					
Contact IRT	X	After the participants meet all eligibility criteria, sites will use IRT for participant number assignment. Register in IRT to obtain participant number. Subsequent visits will be registered into the IRT system for drug supply. See Section 5.1.1. If the IRT system is not available, participants will be enrolled manually. The participant number will be created in the IRT system upon availability.					
Inclusion/Exclusion Criteria	X	Must be confirmed prior to randomization/treatment assignment. See Section 6.1 and Section 6.2.					
Medical History	X	All medical history relevant to the disease under study. Include any toxicities or allergies related to previous treatments.					
Prior Cancer Therapies	X						

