Table 2-2: On Treatment - Schedule of Activities for Q4W Treatment Administration in Part 1A, Part 1B, Part 2A Arm E, Part 2A Arm F, and the Nivolumab Maintenance Phase of Part 2A Arms A and D

Procedure		Cy (28 Days	cle 1 in Lengt	h)	(2	Cyc 28 Days i	ele 2 in Lengtl	h)	Cycles 3 ^a and Beyond (Each Cycle 28 Days in Length)	EOT ^{b,c}	Notes
	D1	D8 (± 2 days)	D15 (± 2 days)	D22 (± 2 days)	D1 (± 2 days)	D8 (± 2 days)	D15 (± 2 days)	D22 (± 2 days)	D1 (± 2 days)		
											dose. All other cycles collected prior to dosing.
PRO-CTCAE	X	X	X	X	X	X	X	X	X	X	For C1D1, performed after randomization but prior to first dose. All other cycles collected prior to dosing.

Abbreviations: ADA = anti-drug antibody; AE = adverse event; BMS = Bristol Myers Squibb; CT = computed tomography; CXDY = Cycle X Day Y, as an example; D = day; ECG = electrocardiogram; ECOG = Eastern Cooperative Oncology Group; EORTC QLQ-C30 = European Organisation for Research and Treatment of Cancer Quality of Life Questionnaire - Core 30; EOT = end of treatment; EQ-5D-3L = European Quality of Life - 5 Dimension - 3 Level Questionnaire; FACIT GP5 = Functional Assessment of Chronic Illness Therapy General Physical item 5; hCG = human chorionic gonadotropin; MRI = magnetic resonance imaging; PCWG3 = Prostate Cancer Working Group 3; PD-L1 = programmed death ligand-1; PE = physical examination; PK = pharmacokinetic; PRO-CTCAE = Patient-Reported Outcomes version of the Common Terminology Criteria for Adverse Events; Q4W = every 4 weeks; Q8W = every 8 weeks; Q12W = every 12 weeks; RECIST = Response Evaluation Criteria in Solid Tumors; SAE = serious adverse event; SARS-CoV-2 = severe acute respiratory syndrome coronavirus 2; WOCBP = women of childbearing potential.

Protocol Amendment No.: 09

^a For Part 2A Arm A and Arm D, the first dose of nivolumab monotherapy maintenance will be C5 of treatment, hence Table 2-2 activities should start under column "Cycles 3 and beyond." For Part 2A Arm A and Arm D, C5 nivolumab monotherapy maintenance begins 3 weeks after C4 of the combination dose, refer to Table 2-3. Part 2A Arm A and Arm D participants who do not complete all scheduled combination therapy cycles will not be eligible for the nivolumab monotherapy Maintenance Phase and should enter follow-up (Table 2-5).

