- Arm A: 240 mg BMS-986249 in combination with 360 mg nivolumab administered IV Q3W for 4 doses (Combination Therapy Phase) as a co-administration, followed by 480 mg nivolumab monotherapy administered IV over approximately 30 minutes Q4W (Maintenance Phase), which will begin 3 weeks after the last combination dose.
- Arm B: 800 mg BMS-986249 administered IV Q8W in combination with 480 mg nivolumab administered IV Q4W. Co-administration will continue on cycles where both study treatments are scheduled, while nivolumab will be administered IV over approximately 30 minutes when scheduled as a monotherapy.
- Arm C: 1,200 mg BMS-986249 administered IV Q8W in combination with 480 mg nivolumab administered IV Q4W. Co-administration will continue on cycles where both study treatments are scheduled, while nivolumab will be administered IV over approximately 30 minutes when scheduled as a monotherapy.
- Arm D: 3 mg/kg ipilimumab in combination with 1 mg/kg nivolumab administered IV Q3W for 4 doses (Combination Therapy Phase), followed by 480 mg nivolumab monotherapy administered IV over approximately 30 minutes Q4W (Maintenance Phase), which will begin 3 weeks after the last combination dose. Nivolumab and ipilimumab will be administered sequentially as 2 separate IV infusions. Nivolumab will be given first, over approximately 30 minutes, followed by ipilimumab over approximately 30 minutes, beginning approximately 30 minutes after completion of the infusion of nivolumab.
- Arm E: 480 mg nivolumab monotherapy administered IV over approximately 30 minutes Q4W.
- Addendum Per Revised Protocol 07: Part 2A Arm A, Arm B, and Arm E are discontinued for further enrollment/randomization. The modification of enrollment/randomization in Part 2A is not a consequence of changes in the safety or tolerability profile or benefit/risk assessment of BMS-986249 (see Section 5.5.4). Currently active participants in these arms will continue treatment as assigned and may remain on treatment until protocol-defined discontinuation criteria have been met. In accordance with Revised Protocol 07, participants in Part 2A will be randomized across the study approximately 1:1:1 between 3 treatment arms:
 - Arm C: described above
 - Arm D: described above
 - Arm F: 600 mg BMS-986249 administered IV Q4W in combination with 480 mg nivolumab administered IV Q4W as a co-administration.

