5.1.4 Window Visits

A \pm 2 day window is permitted to accommodate study participants and schedules during and between cycle visit days for all treatment visits, except for Cycle 1 Day 1.

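### Before Week 12 Arm D has one more QLQ-C30 form than Arms C and F, so the all-visits time-to-deterioration hazard ratio can lean modestly toward BMS-986249 when scores are noisy

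*Combined protocol and SAP*

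**What the plan says.** Tables 1-2 and 4-2 list TTD in global health status/QoL and in physical functioning as a Part 2A secondary endpoint. Table 10.3.7-1 defines it as "defined as the time from randomization until a clinically meaningful decline (ie, reduction ≥10 points) from baseline in EORTC QLQ-C30" and adds: "The analysis will use all available data from randomized participants, including data collected during post-treatment follow up". The summary is: "Median deterioration times, hazard ratios, and 95% CIs will be calculated". The section states no confirmation rule, no common visit window and no interval-censored method, and it does not say which arms each hazard ratio compares. It closes with: "Further exploratory analyses for Part 2A and Part 2B not specified here will be described in the Statistical Analysis Plan".

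The forms follow the dosing cycle. In Table 2-3 Arm D completes the QLQ-C30 before dosing on Day 1 of four 21-day cycles. Table 2-2, footnote a, then says "C5 nivolumab monotherapy maintenance begins 3 weeks after C4 of the combination dose". Tables 2-2 (Arm F) and 2-4 (Arm C) collect it on Day 1 of 28-day cycles.

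The grid is nominal. If a dose is late, Section 2 says assessments "should be correspondingly delayed with the exception of tumor assessments", so questionnaires move with the dose. Section 5.1.4 adds that a ±2 "day window is permitted to accommodate study participants and schedules during and between cycle visit days for all treatment visits", apart from Cycle 1 Day 1.

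**The concern.** Under a first-drop rule every extra form is an extra chance to record a drop of 10 points or more. If scores vary from visit to visit for reasons unrelated to treatment, the arm with more early forms collects more chance events. Here that arm is the comparator, ipilimumab plus nivolumab.

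The first 12 weeks also matter clinically. Section 5.5.1.3 places most ipilimumab immune-related events there, so early forms cannot simply be discarded. Part 2A asks whether BMS-986249 is better tolerated than ipilimumab. A TTD hazard ratio below 1 would be read as patient-reported support for that, when part of it could come from the visit calendar.

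**Working it through.** **No plan figure to reproduce.** The documents give no event count, power, score SD, correlation or expected hazard ratio for TTD. The comparisons C versus D and F versus D are assumed from the Part 2A objectives.

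**1. Nominal grids, weeks from first dose.**
- Arm D: 3, 6, 9, then 9 + 3 = 12, then 16, 20 and so on.
- Arms C and F: 4, 8, 12, 16 and so on.
- Cumulative forms, D against C/F: Week 9, 3 v 2; Week 12, 4 v 3; Week 24, 7 v 6; Week 52, 14 v 13.

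**2. Noise.** If each form had an independent chance p of a spurious drop, the chance of at least one by Week 12 would be 1 − (1 − p)^4 in Arm D and 1 − (1 − p)^3 in C/F. Arm D's is larger for any p between 0 and 1.

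**3. A lasting drop.** It is recorded at the first form at or after onset.

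| Onset (weeks) | Arm D form | C/F form | Recorded first |
|---|---|---|---|
| 0-3 | 3 | 4 | D |
| 3-4 | 6 | 4 | C/F |
| 4-6 | 6 | 8 | D |
| 6-8 | 9 | 8 | C/F |
| 8-9 | 9 | 12 | D |
| 9-12 | 12 | 12 | tie |

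That is D for 3 + 2 + 1 = 6 weeks, C/F for 1 + 2 = 3 and a tie for 3. For evenly spread onset the mean lag to the next form is 3/2 = 1.5 weeks (D) against 4/2 = 2.0 (C/F), a difference of half a week.

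**4. Hazard ratio with identical QoL.** All inputs are assumed: visit-error SD 7 or 10, 4-week correlation 0 or 0.5, mean change none or −3 by Week 12, continuous or stepped scores, follow-up to Week 36 or 52. The model is Cox with Efron ties, and Monte Carlo error is about ±0.02.

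| Case | All visits | Matched visits |
|---|---|---|
| Nominal grid, independent errors | 0.87-0.95 | 0.98-1.03 (both rows) |
| Nominal grid, correlation 0.5 | 0.92-0.99 | |
| ±2 days and delays, independent errors | 0.87-0.95 | 0.97-1.06 (both rows) |
| ±2 days and delays, correlation 0.5 | 0.92-1.00 | |
| Delays and early stops, independent errors | 0.89-0.96 | 0.97-1.07 (both rows) |
| Delays and early stops, correlation 0.5 | 0.94-1.00 | |

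Delays are one of 1-3 weeks in 10-50% of Arm D and 10-30% of C/F. Early stops are 36.4% of Arm D (a rate borrowed from Table 5.4.7.1-1) and 0, 16 or 36% of C/F, followed by the Day 30, 60 and 100 visits. Restricting the nominal grid to Week 12 onward gives 0.97-1.02, which isolates the early grid as the cause.

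The lean fades as noise falls. At correlation 0.8 separate runs gave 0.97-0.99, and at 0.9, 0.98-1.00. For lasting deterioration with median onset 4, 8, 13 and 26 weeks, the all-visits figures are 0.89, 0.96, 0.98 and 0.99.

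**5. Against sampling error.** The log-HR standard error at 60 per arm is 0.21-0.31. At the extremes |ln 0.87|/0.21 = 0.139/0.21 = 0.7 and |ln 0.92|/0.21 = 0.083/0.21 = 0.4. The 95% CI wrongly favours C/F in 4.5-10.3% of null trials with independent errors and 2.7-4.4% at correlation 0.5, against a nominal 2.5%. Matched visits give 1.8-3.2%. A different score model gave 5.1-5.7% in favour of BMS-986249 and 1.1-1.5% in favour of Arm D.

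**6. Reversal.** If 30% or 50% of onsets fall in Weeks 3-4, the all-visits HR is 1.08 or 1.25 (matched 1.11 or 1.31). If they fall in Weeks 6-8, it is 1.10 or 1.27 (matched 1.00 in both).

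**7. Window rule.** Take windows from 14 days before to 13 days after Weeks 4, 8 and 12: Days 14-41, 42-69 and 70-97. Arm D's nominal forms are on Days 21, 42, 63 and 84. Day 42 lies 14 days and Day 63 lies 7 days from Day 56, so Day 63 is used and Day 42 is not. A C/F participant delayed 2 weeks before dose 2 has forms on Days 42, 70, 98 and so on, each in its own window. A rule keeping only forms strictly less than 14 days from a target would discard all of these, so the half-open boundary matters.

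**The case against.** **The SAP may already settle this.** Section 10.3 calls itself a summary, and Section 10.3.1 leaves further calculation detail for time-to-event endpoints to the SAP, giving DOR and PFS as examples. The separate SAP text is not in the combined document. This stands. A reader might infer that the plan has no windowing or confirmation rule at all, but the documents show only that Section 10.3.7 states none.

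**The 6-to-3 count overstates the effect.** This also stands. The mean lag differs by half a week, and lasting deterioration gives almost no lean unless onset is very early. The extra noisy look does most of the work.

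**The size is assumed.** True: score variability and correlation are not in the documents, and strong correlation brings the hazard ratio close to 1.

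**Matching is not clearly better in every case.** With delays and early stops at correlation 0.5, all-visits gives 0.94-1.00, while matched values over those stop runs reach about 1.07. For onsets clustered in Weeks 3-4 matching is slightly worse. That is why it belongs beside the planned analysis and not in its place.

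**The consequence is small.** TTD is secondary, Section 10.1.2.2 calls the design exploratory, and mean QLQ-C30 scores are also planned. This sets the weight of the point but does not remove it, because the stated rule itself produces the lean when scores are noisy.

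**Conclusion.** The point holds as a minor one. The difference in nominal schedule is exact: three forms against two before Week 12, and a common grid afterwards. Its effect on the hazard ratio is conditional. With visit-to-visit noise and no true difference, C/F versus D averages about 0.87-0.95 with independent errors and 0.92-1.00 at a 4-week correlation of 0.5. It is close to 1 at correlation 0.8 or more, or for lasting deterioration that does not start very early. It stays below one standard error at 60 per arm and can reverse if onsets cluster in Weeks 3-4 or 6-8.

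This rests on assumed score variability, delays and stopping, and on the assumed C versus D and F versus D comparisons. A reader might infer that any TTD advantage for BMS-986249 would be an artefact of the calendar. The documents do not support that: the lean is small against sampling error, its direction is not guaranteed, and the primary endpoints do not use these forms.

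**What to change.** In Section 10.3.7 and the SAP, name the comparisons (C versus D, F versus D), keep the all-visits TTD, and pre-specify a matched-visit sensitivity analysis:

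- Use contiguous half-open 4-week windows centred on Weeks 4, 8, 12, 16 and so on, from 14 days before to 13 days after each target, with days counted from Cycle 1 Day 1. Every form from Day 14 onward then falls in exactly one window, and participants with delayed doses are not dropped.
- Use one form per window, the nearest to the target (the earlier if tied), and date the event at the nominal week.
- Add a Week-12-onward sensitivity analysis on the same windows.
- Report the hazard ratios together and state that an advantage seen only in the all-visits analysis may reflect the visit schedule.

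The cost is SAP wording and one extra table on data already collected. Usually one Arm D form (Week 6) goes unused. Weeks 3/4 and 9/8 remain a week apart, and an Arm D event at Week 9 is dated Week 8. On the nominal grid the arms then tie for 10 of the 12 onset weeks, with one week favouring each side. If Arm D has more delays or early stops, the matched hazard ratio can lean slightly the other way, up to about 1.07.
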